4. INVESTIGATIONAL PLAN

4.1. Overall Study Design

This is an open-label, monotherapy study of INCB054828 in subjects with advanced/metastatic or surgically unresectable cholangiocarcinoma with FGFR2 translocations, with other FGF/FGFR alterations, or who are negative for FGF/FGFR alterations. The study will enroll approximately 140 subjects total: 100 subjects with FGFR2 translocations (Cohort A), 20 subjects with other FGF/FGFR alterations (Cohort B), and 20 subjects with no FGF/FGFR alterations (Cohort C [US only]).

Subjects will receive a once daily dose (QD) of INCB054828 at 13.5 mg on a 2-week-on therapy and 1-week-off therapy schedule. Full study drug administration information can be found in Section 5.2.

Subject eligibility can be based on local genomic testing results, if available. Confirmatory testing through the central genomics laboratory will be performed on all subjects.

Previous therapies may include chemotherapeutic agents, immunotherapies, with or without radiotherapy. Subjects receiving radiotherapy to target lesion(s) must show progression of target lesion before entry into the study.

[figure not shown]
Genomic testing results will allow subjects to be assigned to a cohort:

- Cohort A: FGFR2 translocations with a documented fusion partner in central laboratory report
- Cohort B: other FGF/FGFR alterations
- Cohort C (US only): negative for FGF/FGFR alterations

Subjects enrolled based on a local sequencing report will be assigned to a cohort based on the local results. However, final cohort assignment for statistical analysis of primary and secondary endpoints will be done based on the central genomics testing results.

Treatment will start on Cycle 1 Day 1. Subjects will undergo regular safety assessments during treatment as well as regular efficacy assessments. Subjects will be allowed to continue administration in 21-day cycles until documented disease progression or unacceptable toxicity is reported. See Figure 3 for the study design.

Figure 3: Study Design

D/C = discontinue; SF = screen fail.

4.2. Measures Taken to Avoid Bias

This is an open-label study; no comparisons will be made between subjects or against historical controls. Measurements of safety and efficacy are objective measurements, and only comparisons to pretreatment conditions will be made.

4.3. Number of Subjects

4.3.1. Planned Number of Subjects

Approximately 140 subjects (total) are planned for enrollment. This may vary due to outcome of fertility analysis.

4.3.2. Replacement of Subjects

Not applicable.

4.4. Duration of Treatment and Subject Participation

After signing the ICF, screening assessments may be completed over a period of up to 28 days. Each subject enrolled in the study may continue to receive study treatment in continuous 21-day cycles. At the point when the subject discontinues study drug (INCB054828), the treatment period will end and the subject will enter the follow-up period (see Section 6.4). Study participation is expected to average approximately 6 months per individual subject.

4.5. Overall Study Duration

The study begins when the first subject signs the ICF. The end of the study will occur when all subjects have discontinued study drug and have completed applicable follow-up assessments.

If there have been ≤ 2 subjects on study for more than 8 months, then a database lock of the study may occur to allow the analysis of the study data. Any remaining subjects may continue to receive study treatment per Protocol. The remaining subjects are considered to be on study until a discontinuation criterion is met and written notification is provided to the sponsor.

4.6. Study Termination

The investigator retains the right to terminate study participation at any time, according to the terms specified in the study contract. The investigator is to notify the institutional review board (IRB)/independent ethics committee (IEC) in writing of the study's completion or early termination, send a copy of the notification to the sponsor or sponsor's designee, and retain 1 copy for the site study regulatory file.

The sponsor may terminate the study electively, if required by regulatory decision, or upon advice of the study committee. If the study is terminated prematurely, the sponsor will notify the investigators, the IRBs and IECs, and regulatory bodies of the decision and reason for termination of the study.

5. TREATMENT

5.1. Treatment Assignment

5.1.1. Subject Numbering and Treatment Assignment

The interactive response technology (IRT) will be contacted at the beginning of screening to obtain a subject number. All subject numbers will be 6 digits; the first 3 digits will be the site number, and the last 3 digits will be the subject's number. This subject number will be maintained throughout the study and will not be reassigned. Subjects who withdraw consent or discontinue from the study after being assigned a subject number will retain their initial number.

Site staff will contact the IRT after screening is completed to enroll the subject and to allocate the subject to treatment assignment and obtain the initial study drug assignment. The investigator or designee will select the appropriate number of bottles of study drug from their stock that correspond to the dose provided by the IRT and dispense the study drug to the subject. All subsequent dispensing of study drug should follow this process. Refer to the IRT manual for detailed information.

If a subject is mistakenly given a bottle of study drug that is not the bottle assigned by the IRT, the IRT help desk must be notified immediately. The reason for the misallocation of the study drug must be documented by the study site and reported to the IRB/IEC.

For subjects who signed an ICF but are not allocated and for subjects who are allocated but were not treated, refer to the electronic case report form (eCRF) Completion Guidelines for instruction on which eCRFs to complete.

All subjects will receive the same treatment assignment (13.5 mg QD) regardless of cohort assignment.

5.1.2. Randomization and Blinding

Not applicable, since this is an open-label, single-group study.

5.2. Study Drug

5.2.1. INCB054828

5.2.1.1. Description and Administration

INCB054828 will be self-administered as a QD oral treatment on a 21-day cycle. Subjects will take study drug for 2 weeks continuously (14 days) followed by a 1-week (7 days) break. The starting dose will be 13.5 mg. Each dose of study drug should be taken immediately upon rising or after a 2-hour fast. Subject should plan to fast for 1 additional hour after taking study drug.

5.2.1.2. Supply, Packaging, and Labeling

Study drug will be supplied as 2 mg and 4.5 mg tablets. All tablet excipients comply with the requirements of the applicable compendial monographs (Ph Eur, USP-NF; refer to the [IB](#)).

INCB054828 tablets will be packaged in high-density polyethylene bottles. No preparation is required.

All Incyte investigational product labels will be in the local language and will comply with the legal requirements of each country.

5.2.1.3. Storage

Bottles of tablets should be stored at room temperature, 15°C to 30°C (59°F to 86°F).

5.2.1.4. Instruction to Subjects for Handling Study Drug (INCB054828)

The subject must be instructed in the handling of study drug as follows:

- To store the study drug at room temperature.
- To only remove from the study drug bottle the number of tablets needed at the time of administration.
- Not to remove doses in advance of the next scheduled administration.
- Tablets cannot be split or crushed
- To make every effort to take doses on schedule.
- To report any missed doses.
- To take study drug immediately upon rising or after a 2-hour fast with a glass of water; the subject should refrain from eating 1 hour after taking study drug.
- If the subject vomits after taking study drug, the subject should not take another dose that day.
- To keep study drug in a safe place and out of reach of children.
- To bring all used and unused study drug kits to the site at each visit.
- If a dose of INCB054828 is missed by more than 4 hours, that dose should be skipped and the next scheduled dose should be administered at the usual time.

5.3. Treatment Compliance

Compliance with all study-related treatments should be emphasized to the subject by the site personnel, and appropriate steps should be taken to optimize compliance during the study.

Compliance with INCB054828 will be calculated by the sponsor based on the drug accountability documented by the site staff and monitored by the sponsor/designee (tablet counts). Subjects will be instructed to bring the study drug with them to the study visits in order for site personnel to conduct tablet counts to assess study drug accountability. The drug accountability documentation will be used by the sponsor to calculate treatment compliance.

5.4. Treatment Interruptions and Adjustments

5.4.1. Dose Modifications

Dose interruptions and modifications may occur for individual study subjects. The occurrence of toxicities (related or unrelated to study drug) will guide decisions for treatment interruptions and discontinuation for individual subjects.

5.4.2. Criteria and Procedures for Dose Interruptions and Adjustments of Study Drug

Treatment with INCB054828 may be delayed up to 14 days to allow for resolution of toxicity (Table 3). Subjects may resume treatment if no medical condition or other circumstance exists that, in the opinion of the investigator, would make the subject unsuitable for further participation in the study. The treating investigator should contact the sponsor to discuss the case of any subject whose treatment has been delayed for more than 14 days before restarting treatment with INCB054828.

Table 3: Guidelines for Interruption and Restarting of Study Drug

ADVERSE EVENT	ACTION TAKEN
Chemistry	

 • AST and/or ALT is $> 5.0 \times \text{ULN}$. Note: In subjects with liver metastasis-related elevations at baseline, contact sponsor to discuss clinical management and possible dose reductions.	
Step 1: Interrupt study drug up to 2 weeks (14 days) until the toxicity has resolved to \leq Grade 1 except by approval of the medical monitor.
 
Step 2: Restart study drug at same dose. If assessed as related to study drug, restart study drug at next lower dose; monitor as clinically indicated.

Other toxicities, including SRD/RPED	

 • Any Grade 1 or Grade 2 toxicity. 	Continue study drug treatment and treat the toxicity; monitor as clinically indicated.

 • Any Grade 3 toxicity, if clinically significant and not manageable by supportive care. 	
Step 1: Interrupt study drug up to 2 weeks (14 days), until toxicity resolves to \leq Grade 1.
 
Step 2: Restart study drug at same dose. If assessed as related to study drug, restart study drug at next lower dose; monitor as clinically indicated.

 • Any recurrent Grade 3 toxicity after 2 dose reductions. 	Discontinue study drug administration and follow-up per Protocol. (Exceptions require approval of sponsor.)

 • Any other Grade 4 toxicity. 	Discontinue study drug administration and follow-up per Protocol.

For subjects who present with possible or confirmed serous retinal detachment/retinal pigmented epithelium detachment (SRD/RPED) based on optic coherence tomography (OCT), the guidelines in Table 3 should be followed. It is recommended to discuss the findings with the Incyte medical monitor before making changes to the subject's treatment.

Per CTCAE v4.03, there is a grading for retinal detachment; however, this refers to rhegmatogenous retinal detachment (when a hole occurs in the retina) or exudative detachment (fluid accumulation due to inflammatory diseases). There is no exact CTCAE grading term for SRD/RPED secondary to FGFR inhibition (there is no hole in the macula, just fluid accumulation or detachment of retinal pigmented epithelium). Therefore, grading should be based on the CTCAE term "retinopathy."

Due to the fact subjects may enter the study with extensive pretreatment toxicities, the dose reduction rules are provided as guidelines (see [Table 3](#)).

For dose adjustments, the sponsor recommends a maximum of 2 dose level reductions: subjects administered 13.5 mg can decrease to 9 mg, and if additional dose reduction is required, subjects can decrease to 6 mg. Dose reductions below 6 mg are not allowed. The frequency of administration remains the same (once daily) and as well as the schedule (2 weeks on treatment followed by 1 week off treatment).

Adverse events that have a clear alternative explanation or transient (≤ 72 hours) abnormal laboratory values without associated clinically significant signs or symptoms may be exempt from dose-reduction rules.

5.4.3. Management of Hyperphosphatemia

Hyperphosphatemia is an expected on-target pharmacologic effect of FGFR inhibition. Hyperphosphatemia should be managed with diet modifications, phosphate binders and diuretics, or a dose reduction per the recommendations in [Table 4](#).

Table 4: Recommended Approach for Hyperphosphatemia Management

Serum Phosphate Level	Supportive Care	Guidance for Interruption/Discontinuation of INCB054828	Guidance for Restarting INCB054828
> 5.5 mg/dL and ≤ 7 mg/dL	Initiate a low-phosphate diet	No action.	Not applicable.
> 7 mg/dL and ≤ 10 mg/dL	Initiate/continue a low-phosphate diet and initiate phosphate-binding therapy once serum phosphate level is > 7 mg/dL. Monitor serum phosphate at least twice a week and adjust the dose of binders as needed; continue to monitor serum phosphate at least twice a week until return to ≤ 7 mg/dL.	If serum phosphate level continues to be > 7 mg/dL and ≤ 10 mg/dL with concomitant phosphate-binding therapy for 2 weeks, or if there is recurrence of serum phosphate level in this range, interrupt INCB054828 for up to 2 weeks (not including the planned dose interruption per treatment cycle).	Restart at the same dose when serum phosphate is ≤ 7 mg/dL. If serum phosphate level recurs at > 7 mg/dL, restart study drug with dose reduction.
> 10 mg/dL	Continue to maintain a low-phosphate diet, adjust phosphate-binding therapy, and start/continue phosphaturic agent. Continue to monitor serum phosphate at least twice a week until return to ≤ 7 mg/dL.	If serum phosphate level is > 10 mg/dL for 1 week following phosphate-binding therapy and low phosphate diet, interrupt study drug. If there is recurrence of serum phosphate level in this range following 2 dose reductions, permanently discontinue INCB054828.	Restart study drug at reduced dose with phosphate binders when serum phosphate is ≤ 7 mg/dL.

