- Documented disease progression after at least 1 line of prior systemic therapy.
- ECOG performance status of 0 to 2.
- Life expectancy \geq 12 weeks.

Key Exclusion Criteria:

- Prior receipt of a selective FGFR inhibitor.
- History of and/or current evidence of ectopic mineralization/calcification, including but not limited to soft tissue, kidneys, intestine, myocardia, or lung, excepting calcified lymph nodes and asymptomatic arterial or cartilage/tendon calcifications.
- Current evidence of clinically significant corneal or retinal disorder confirmed by ophthalmologic examination.
- Use of any potent CYP3A4 inhibitors or inducers within 14 days or 5 half-lives, whichever is shorter, before the first dose of study drug. Topical ketoconazole will be allowed.

INCB054828, Dosage, and Mode of Administration:

INCB054828 will be self-administered as a QD oral treatment on a 2-weeks-on therapy and 1-week-off therapy schedule. Each dose of INCB054828 should be taken immediately upon rising or after a 2-hour fast; subjects will fast for an additional 1 hour after taking study drug. Tablets will be available in strengths of 2 mg and 4.5 mg. The starting dose will be 13.5 mg. One cycle will be defined as 21 days.

Reference Therapy, Dosage, and Mode of Administration:

Not applicable.

Study Schedule/Procedures:

Subjects will have regularly scheduled study visits at the clinical site as part of a 21-day cycle. Study visits are as follows:

- Prescreening: To obtain FGF/FGFR status, if unknown (results within approximately 2 years of screening are valid for this study)
- Screening: Day -28 through Day -1
- Cycle 1: Days 1, 8, and 15
- Cycles 2+: Day 1
- End of treatment
- Safety follow-up: 30 days (+ 5 days) from date of last dose
- Follow-up for disease status and survival: Disease status follow-up every 9 weeks for subjects who discontinue for reasons other than disease progression. Survival follow-up every 12 weeks after discontinuation.

Local Laboratory Tests:

Study visits will include sample collection for hematology, chemistry, coagulation, endocrine monitoring, lipids, and urinalysis testing. Additionally, HIV screening (required for subjects outside of the US) and hepatitis screening (serology) will be done at screening; pregnancy testing will be done at screening, Day 1 of every cycle before dose administration, and EOT. FGF/FGFR status may be determined locally.

Central Laboratory Assessments:

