1.3.2.1. Pharmacokinetic/Pharmacodynamic Summary

INCB054828 exhibited linear PK over the dose range evaluated, with rapid oral absorption and a biphasic elimination, with a terminal half-life range of 10.9 to 31.4 hours. The projected average inhibition of FGFR2 based on PK and *in vitro* potency of INCB054828 ranged from 41% at 1 mg to 97% at 20 mg. Consistent with this projection, the observed inhibition of pFGFR2 in KATOIII cells spiked to *ex vivo* whole blood samples collected from subjects at trough was 82% after the 13.5 mg QD dose and 64% after the 9 mg QD dose. The steady-state plasma concentrations of INCB054828 after 13.5 mg QD dose that exceeded *in vivo* IC₅₀ over a 24-hour dosing period is showed in [Figure 1](#). The magnitude and frequency of HP was also dose-dependent. In the 9 mg cohort, 1 of 3 subjects developed HP in Part 1; 3 additional subjects were enrolled at 9 mg in Part 2. Of a total of 6 subjects administered 9 mg, 4 experienced HP; in the 13.5 mg cohort, all 6 subjects developed HP, which was managed with a low-phosphate diet and introduction of phosphate binders. Further, the increase in serum phosphorus observed after treatment with INCB054828 was exposure-dependent (see [Figure 2](#)).

Figure 1: INCB054828 Plasma Concentrations (Mean \pm SE) at Steady State After 13.5 mg QD Oral Doses of INCB054828

[figure not shown]
[figure not shown]

Figure 2: Serum Phosphate Versus Exposure

Therefore, based on a manageable safety profile and a favorable PK/PD profile, the targeted starting dose for this Phase 2 is 13.5 mg. This dose will be tested in 2 additional Phase 2 studies in subjects with bladder cancer (INCB 54828-201) and myeloproliferative neoplasms (INCB 54828-203).

Subjects will be monitored on an ongoing basis throughout this study as per the schedules of assessments (Table 5 and Table 6).

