				Cycle 1			Cycles 2+			
				Day 1	Day 8 (± 3 Days)	Day 15 (± 3 Days)				
Serum chemistries	7.5.6		X	X*	X	X	X	X	* May be performed within 3 days of the first dose.	
Hematology	7.5.6		X	X*	X	X	X	X	* May be performed within 3 days of the first dose.	
Lipid panel	7.5.6			X				X		
Endocrine	7.5.6		X	X			X	X		
Coagulation panel	7.5.6		X				X*	X	* Only every 3 cycles starting at Cycle 3.	
Hepatitis screening	7.5.6.2		X							
Urinalysis	7.5.6		X				X*		* Only every 3 cycles starting at Cycle 3.	
Pregnancy test	7.5.6.1		X*	X**			X**	X**	* Serum ** Day 1 of each cycle; urine pregnancy test allowed.	
HIV testing	7.5.6.3		X*						* Optional for US subjects.	
Central laboratory										
Blood sample for PK	7.7				X*					Samples will be drawn at predose, 1-2 hours postdose, and 4-12 hours postdose (3 samples total). *Subject must fast 8 hours before first sample (predose).
Tumor tissue sampling/archival tissue	7.8	X*					X**			* Slides or FFPE block must be provided. ** Optional on-treatment or EOT biopsy, such as disease progression after complete or PR.

Table 7: Laboratory Tests: Required Analytes

Serum Chemistries	Hematology	Urinalysis With Microscopic Examination	Hepatitis Screening	Coagulation
Albumin Alkaline phosphatase ALT AST Bicarbonate (not in Japan) Blood urea nitrogen or urea Calcium Chloride Creatinine Glucose Lactate dehydrogenase Phosphate Potassium Sodium Total bilirubin Direct bilirubin (if total bilirubin is elevated above ULN) Total protein Uric acid Vitamin D (25-hydroxyvitamin D and 1,25-dihydroxyvitamin D)	Complete blood count, including: Hemoglobin Hematocrit Platelet count Red blood cell count White blood cell count Differential count, including: Basophils Eosinophils Lymphocytes Monocytes Neutrophils Absolute values must be provided for: WBC differential laboratory results: Lymphocytes Neutrophils	Color and appearance pH and specific gravity Bilirubin Glucose Ketones Leukocytes Nitrite Occult blood Protein Urobilinogen	Hepatitis B surface antigen Hepatitis B surface antibody Hepatitis B core antibody HCV antibody NOTE: If any of the above are positive, HBV-DNA, HCV-RNA to assess risk of reactivation.	PT PTT or aPTT INR
		Lipid Panel	Other	Pregnancy Testing

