4.1.5. Cycle Length and Duration

Cycle 1 Day 1 is the day that the first dose of INCB054828 is administered. Scheduled cycle length is 21 days, with first day of each cycle corresponding with the first day of INCB054828 administration in that cycle.

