4.1.6. Analysis Window

For parameters that will be summarized by visit, the nominal visit as recorded on the eCRF will be used. There will be no additional analysis windowing done based on the assessment date.

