8.3.2. Laboratory Value Summaries

All test results and associated normal ranges from central laboratories will be reported in SI units. All tests with numeric values will have a unique unit per test. Any laboratory test results and associated normal ranges from local laboratories will be converted to SI units.

For numeric laboratory values, baseline value, postbaseline value, change from baseline, and percent change from baseline will be summarized by visit. In addition, mean change from baseline will be plotted over time for selected laboratory parameters, including phosphate, calcium, sodium, 1,25-dihydroxyvitamin D, 25-hydroxyvitamin D, and parathyroid hormone.

For the laboratory parameters that have CTCAE grading, shift tables will also be presented showing change in CTCAE severity grade from baseline to worst grade postbaseline. The

denominator for the percentage calculation will be the number of subjects in the baseline category.

Categorical laboratory data will be tabulated by visit at baseline and postbaseline visits where appropriate.

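### From Cycle 2 the only scheduled phosphate draw before end of treatment follows the drug-free week, so no draw is required on drug to look for recurrence once phosphate is ≤ 7 mg/dL, and the planned mean-change plot mixes dosing phases

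*Protocol*

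**What the plan says.** **Dosing.** Protocol 5.2.1.1: "Subjects will take study drug for 2 weeks continuously (14 days) followed by a 1-week (7 days) break". SAP 4.1.5 fixes the cycle length at 21 days, "with first day of each cycle corresponding with the first day of INCB054828 administration in that cycle".

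**Sampling.** Phosphate is one of the serum chemistry analytes in protocol Table 7. The synopsis gives the visits as "Cycle 1: Days 1, 8, and 15", then Day 1 only for later cycles; Table 5 allows ± 3 days. In Table 6 the row "Serum chemistries" is marked at screening, the three Cycle 1 visits, once per cycle from Cycle 2, and EOT.

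**Triggered sampling.** Table 4 adds phosphate draws at least twice a week once a value exceeds 7 mg/dL. In the row for values above 7 and up to 10, sites are to "continue to monitor serum phosphate at least twice a week until return to ≤ 7 mg/dL"; the row above 10 has the same end point. Recurrence in the range from above 7 to 10 leads to interruption. Recurrence above 10 after two dose reductions leads to permanent discontinuation.

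**Pharmacology.** Protocol 1.3.2.1 gives a terminal half-life of 10.9 to 31.4 hours and says that "the increase in serum phosphorus observed after treatment with INCB054828 was exposure-dependent".

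**Analysis.** SAP 8.3.2: "mean change from baseline will be plotted over time for selected laboratory parameters, including phosphate". For parameters summarised by visit, SAP 4.1.6 says "the nominal visit as recorded on the eCRF will be used", with no re-windowing by assessment date.

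**The concern.** Two things follow from the position of the Day 1 visit in the cycle.

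First, the value of ≤ 7 mg/dL that ends the extra draws is also the point from which a recurrence is counted, and it may be obtained during the off week. From then on Table 4 acts on recurrence, but no section requires a sample while the subject is taking drug. The same gap applies to a subject who first exceeds 7 mg/dL during a dosing week of Cycle 2 or later. Hyperphosphatemia was the most frequent treatment-emergent event in Parts 1 and 2 of the Phase 1 study (protocol 1.3.2), and all 6 subjects in its 13.5 mg cohort developed it (1.3.2.1). Soft tissue mineralization was not reversible in rats over a 28-day recovery period (1.3.1). The timing of detection is therefore a safety question.

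Second, the phosphate plot confounds time on study with dosing phase. Its two early post-baseline points come from the dosing weeks or the day after them, and all later scheduled points before EOT come after the break. If the line drops at Cycle 2 Day 1, the plot cannot show whether phosphate adapted, was controlled by diet and binders, or was simply sampled at a different phase of the cycle.

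**Working it through.** The plan gives no figure of its own to reproduce. The check is a count of draws against dosing days, followed by the drug remaining at each draw.

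**Inputs.** Dosing on Days 1–14 and break on Days 15–21 (protocol 5.2.1.1). Visits on Cycle 1 Days 1, 8 and 15, then Day 1, ± 3 days (synopsis, Table 5). Half-life 10.9 to 31.4 h (1.3.2.1).

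**Step 1: scheduled draws while dosing, after the first dose of the cycle.**
- Cycle 1: one during dosing (Day 8) and one nominally the day after the last dose (Day 15).
- Each cycle from Cycle 2: none. The Day 1 draw nominally comes at the end of the break.

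**Step 2: time since last dose at the next Day 1.** Day 1 of the next cycle is Day 22 of the current one: (22 − 14) × 24 = 192 h. At the early edge of the window, Day 19: (19 − 14) × 24 = 120 h.

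**Step 3: drug remaining, relative to just after the last dose.** Fraction = 0.5^(hours / half-life). This is a mono-exponential approximation on the terminal half-life; the protocol describes elimination as biphasic.

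| Draw | Half-life 31.4 h | Half-life 10.9 h |
|---|---|---|
| Cycle 1 Day 15 (24 h) | 0.5^0.76 = 58.9% | 0.5^2.20 = 21.7% |
| Next Day 1, 3 days early (120 h) | 0.5^3.82 = 7.1% | 0.5^11.01 = 0.05% |
| Next Day 1, nominal (192 h) | 0.5^6.11 = 1.4% | 0.5^17.61 < 0.01% |

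Against the 24 h trough instead, the nominal Day 1 figure at 31.4 h is 0.5^(168/31.4) = 2.5%.

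**Step 4: make-up of the plotted line.** Taking Cycle 1 Day 1 as baseline and leaving out EOT, the scheduled post-baseline points through Cycle n Day 1 are 2 from Cycle 1 (Days 8 and 15) and n − 1 after the break.
- Through Cycle 3 Day 1: 2 of 4 after the break (50%).
- Through Cycle 5 Day 1: 4 of 6 (67%).
- Through Cycle 9 Day 1: 8 of 10 (80%).

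**Step 5: one subject traced through the rules.** Phosphate exceeds 7 mg/dL on Cycle 1 Day 8; a binder is started and twice-weekly draws begin. A value ≤ 7 is obtained in the off week and the extra draws end. The next scheduled draws are Day 1 of Cycles 2, 3, 4 and so on, each nominally at the end of a break. A Day 1 value above 7 would count as a recurrence, but nothing obliges the site to look in the dosing weeks between.

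**The case against.** The strongest reply is that Table 6 is a minimum and Table 4 adds triggered draws, so the two do not conflict, and that other provisions fill the gap. Laboratory abnormalities that are adverse events are followed until normal or explained (protocol 8.2). Events are assessed at each visit, or more often if necessary (8.1.2). Unscheduled visits (6.6) and additional tests (note to Table 7) are allowed. These provisions permit or extend follow-up, but none requires a sample in a dosing week, so the gap remains.

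Several objections do stand, and they limit the point.

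- A reader might infer that recurrence is never tested on drug. The documents do not support that. Subjects still above 7 mg/dL are drawn at least twice a week, dosing days included, and EOT or unscheduled draws can fall on drug.
- A reader might infer that the Cycle 2+ values are washed-out phosphate values and that any fall in the plot is an artefact. The arithmetic shows washout of drug only. The dependence on exposure in 1.3.2.1 says nothing about the rate of recovery, and no off-drug phosphate time course is given. Table 4 allows an interruption of up to 2 weeks beyond the planned break, so it does not assume that 7 days are enough.
- A reader might take hyperphosphatemia to be the main cause of interruptions and reductions with this drug. Protocol 1.2 reports it as the leading dose-limiting toxicity for a different FGFR inhibitor. The one dose-limiting toxicity reported for INCB054828 in 1.3.2 is Grade 3 stomatitis.
- Pooling all on-drug values into one series would introduce another bias. After Cycle 1 such values would come largely from draws triggered by phosphate above 7 mg/dL.

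The plot is also descriptive and not the only evidence. Hyperphosphatemia is reported by incidence (protocol 9.4.2.1), as a clinically notable event and by time to first event (SAP 8.2.2 and 8.2.3). Protocol 9.4.2.2 adds worst-value shift tables for analytes without CTCAE grades.

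**Conclusion.** The point holds in limited form. From Cycle 2 no scheduled draw before EOT nominally falls in the dosing weeks after the first dose, and none is required there once phosphate is ≤ 7 mg/dL, although Table 4 acts on recurrence. The nominal Day 1 sample is 6.1 to 17.6 half-lives after the last dose, with about 1.4% or less of the drug remaining (up to 7.1% if the visit is 3 days early). The planned plot joins two on-drug or day-after-dose points to a growing majority of off-week points.

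This rests on nominal timing. The documents do not say whether dosing waits for a late Day 1 visit, and a Day 15 visit made 3 days late (96 h after the Day 14 dose) is itself an off-week sample. The size of any fall in phosphate over the break cannot be derived from the documents, so distortion of the plot is a risk, not a demonstrated effect.

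The SAP part is an inexpensive improvement worth making. The protocol part is a request to reconcile passages. Neither is a condition for the primary analysis, since the objective response rate is unaffected.

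**What to change.** **SAP 8.3.2.**
- Label Cycle 2+ Day 1 laboratory points as off-week values, and do not join them to Cycle 1 Days 8 and 15 as one series.
- Summarise phosphate, calcium and vitamin D by days since last dose, taken from the dosing eCRF. This also sorts out early and late visits. Parathyroid hormone has no scheduled Day 8 or Day 15 draw in Table 6, so a matching on-drug series should not be promised for it.
- Show unscheduled results separately, flagged as triggered by high phosphate and therefore selected upward.

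The cost is SAP wording and programming; no new data are needed.

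**Protocol.** Table 4 and Tables 5 and 6 must be reconciled on two matters: when recurrence is looked for, and whether a value taken in the off week ends the extra monitoring. Draw timing, thresholds and actions are for the sponsor to decide. The cost is an amendment or clarification, plus whatever sampling the sponsor then chooses.
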